5 STUDY DESIGN

5.1 Study description

This is a Phase 2A, multicenter, single-arm, OLE study to evaluate the safety, tolerability, and efficacy of rozanolixizumab during long-term treatment of study participants with CIDP from a previous study with rozanolixizumab.

Access to CIDP04 for study participants coming from CIDP01: Study participants from CIDP01 who have completed the Treatment Period (ie, all visits up to Visit 17) without a relapse of CIDP will be offered the opportunity to be directly enrolled into this OLE study. Study participants will enter CIDP04 on the same day as the last study visit in CIDP01: Visit 17. Study participants from CIDP01 who have experienced a relapse of CIDP (during either the Treatment Period or the Observation Period), have been successfully rescued and stabilized with SOC medication and have consented to enter this OLE study, may be assessed for eligibility. The study participants who relapsed during the Treatment Period of CIDP01 will be offered entry into CIDP04 only once CIDP01 study results are available, after the blind has been broken at the end of the study, and it is confirmed they received placebo in CIDP01.

In case the study participants have a gap period between the end of the parent study and the start of this OLE study (ie, last visit in the parent study does not take place on the same day as entry of study CIDP04), a Screening Period of 2 to 5 weeks will be applicable to confirm that the study participant still meets the eligibility criteria for entry in the OLE study and allow for a smooth transition between the treatment used by the study participants during the gap period and the initiation of rozanolixizumab. The CIDP04 study includes a first 24-week Treatment Period (Part 1) followed by a second Treatment Period (Part 2) of up to 52 weeks (or until an Access Program or equivalent is in place, whichever comes first). Entry to the Treatment Period (Part 2) will be contingent to a favorable individual benefit-risk after careful individual assessment has been performed for each study participant completing Treatment Period (Part 1). An 8-week Observation Period will be followed in case of premature termination or after completion of the Treatment Periods (either at end of Part 1 for study participants not continuing in Part 2 or at end

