8.1 Screening, Visit 1 (Weeks -5 to -2)

The Screening Visit is only for study participants with a gap period between the parent study and entry in CIDP04.

The following procedures will be performed at the Screening Visit (or as close as possible to the Screening date):

- Informed consent process including obtaining written informed consent from the study participant
- iRODS assessment
- Query for suicidality (C-SSRS)
- Tuberculosis Signs and Symptoms Questionnaire
- Record study participant demographics
- Verify (to the extent possible with available information at Screening, Visit 1) that study participant fulfills all the inclusion criteria and none of the exclusion criteria
- Medical history update
- Prior and concomitant medications
- Concomitant medical procedures
- Vital signs (taken once during the visit)
- Body weight (Screening weight will be used for calculation of the infusion dose)
- Recording of AEs
- 12-lead ECG
- Full physical examination
- Full neurological examination
- Contact IRT
- Blood sample (the Laboratory Manual will provide guidance on the order of sample collection) for:
 - Clinical laboratory tests (ie, hematology, clinical chemistry, serology [including hepatitis C and hepatitis B virus-antibodies, HIV1, and HIV2], and interferon gamma release assay [IGRA] for active and latent TB)
 - Serum pregnancy test for women of childbearing potential
 - Immunoglobulins (total IgG and IgG subclasses)
 - Vaccination-specific antibody titers (tetanus and influenza Type A)
- Urine sample for urinalysis
- INCAT assessment

- Assessment of grip strength by site personnel
- RT-MRC assessment
- Provide an appointment to the next visit according to the following guidance:
 - For study participants on an IVIg 3- to 6-week regimen, Baseline Visit should occur 1 week before the next planned IVIg dose (according to the Baseline IVIg regimen). However, if that specific date is not possible, the Baseline Visit (Visit 2) could be up to 1 week after that date.
 - Study participants on a 2-week IVIg treatment regimen will continue on their regular schedule for 1 further IVIg treatment until Visit 2. Visit 2 will occur 1 week before the planned IVIg dose. However, if that specific date is not possible, Visit 2 could be up to 1 week after that date.

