8.2.1 Visit 2, Baseline (Week 1)

The following procedures will be performed at Visit 2 (Week 1). If study participant enters CIDP04 at Visit 2 and the assessment was performed at the last visit in the parent study (eg, CIDP01) (or at Visit 16 for NF-L), the assessment will not be repeated and will be marked as "not to repeat" in the list below:

- Informed consent process including obtaining written informed consent from the study participant (for study participants who did not perform Screening Visit [Visit 1])
- PROs should be conducted in the order specified in Section 10.4:
 - iRODS assessment - to be performed before any other assessment (not to repeat)
 - CIDP PRO instrument (not to repeat)
 - Fatigue scale (not to repeat)
 - PGIS (not to repeat)
 - PGIC (not to repeat) - not required for study participants who had a Screening Visit
- Query for suicidality (not to repeat)
- Record study participant demographics (for study participants who did not perform Screening Visit [Visit 1])
- Verify that study participant fulfills all the inclusion criteria and none of the exclusion criteria (for study participants who did not perform Screening Visit [Visit 1])
- Withdrawal criteria assessment
- Medical history update (for study participants who did not perform Screening Visit [Visit 1])
- Prior and concomitant medications (not to repeat)
- Concomitant medical procedures (not to repeat)
- Vital signs (prior to IMP administration, at the end of the infusion, at 2 and 4h after the end of the infusion)
- Body weight assessment (Visit 2 weight will be used for calculation of the infusion dose for study participants without screening visit) (not to repeat)
- Recording of AEs (not to repeat)
- Full physical examination (not to repeat)
- Full neurological examination (not to repeat)

- 12-lead ECG (not to repeat)
- Blood sample (all samples should be taken predose unless otherwise specified; the Laboratory Manual will provide guidance on the order of sample collection) for:
 - Clinical laboratory tests (ie, hematology, clinical chemistry, and IGRA for active and latent TB) (not to repeat)
 - PK of rozanolixizumab (predose and 4h postdose) (not to repeat predose sample if performed at last visit in the parent study)
 - ADA (anti-rozanolixizumab antibodies) (not to repeat)
 - Serum complement (C3, C4) and plasma complement (C3a, C5a)
 - Serum cytokines (predose)
 - Immunoglobulins (total IgG and IgG subclasses) (not to repeat)
 - IgA, IgM, IgE (not to repeat)

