14.2 General statistical considerations

All analyses will be performed using SAS® version 9.2 or later (SAS Institute, Cary, NC, USA). Continuous variables will be summarized by visit (where applicable) with the statistics mean, standard deviation (SD), median, minimum, and maximum. Categorical variables will be summarized by visit (where applicable) with frequency counts and percentages.

Data listings containing all documented data and all calculated data will be generated.

Baseline will be the last nonmissing data collected prior to the first dose of IMP, and measurement-specific Baseline values will be defined in the SAP.

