3.3 Definition of Baseline values

For all study variables, the Baseline values for study participants treated with rozanolixizumab in the parent study (ie, CIDP01) will be the Baseline values from the parent study. For study participants treated with placebo in the parent study, the Baseline values will be the ones present at Baseline in CIDP04 (Visit 2 or if missing, the Screening Visit value (if applicable)). Note this Visit 2 value may be corresponding to the last value registered into CIDP01 as these may be the same visit.

Scheduled or unscheduled measurements can be used as the Baseline value. Expected measurement-specific Baseline timepoints are presented in [Table 3-1](#). If an unscheduled measurement occurs after the planned baseline measurement timepoint but before dosing, then the unscheduled measurement will be used as the baseline value.

Table 3–1: Expected Baseline

Measurement	Definition of Baseline
Safety data: 
• Safety Lab (Clinical chemistry, Hematology, Urinalysis)• ECG• Vital signs• Total protein, albumin, α- and β-globulins	For study participants treated with rozanolixizumab in parent study CIDP01: Safety labs, vital signs, total protein, albumin, α - and β -globulin: Baseline visit (Day 1) of parent study, if missing Screening visit of parent study (pre-dose value, if applicable). For study participants treated with placebo in the parent study: Safety labs, vital signs, total protein, albumin, α - and β -globulin: Baseline visit (Day 1) in CIDP04, if missing Screening visit (if applicable) (pre-dose value, if applicable). ECG: mean of triplicate values of Baseline visit (Day 1) in CIDP04. If missing Baseline visit, mean of triplicate values of Screening visit (if applicable).
Efficacy data 
• iRODS• INCAT• Grip strength (assessed by site personnel)• RT-MRC and original MRC• Fatigue score• CIDP PRO• PGIS• PGIC	For study participants treated with rozanolixizumab in parent study CIDP01: Baseline visit (Day 1) in CIDP01, if missing Screening visit For study participants treated with placebo in the parent study: Baseline visit (Day 1) in CIDP04, if missing Screening visit (where applicable)

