Immunological variables: 
• IgA, IgE, IgM• Serum complement levels (C3, C4),• Plasma complement (C3a, C5a)• ADA• Cytokines• Tetanus- and influenza A virus-specific IgG antibodies	For study participants treated with rozanolixizumab in parent study CIDP01, refer to baseline definition in SAP for the parent study (ie Baseline visit (Day 1) of parent study, except for Tetanus- and influenza A virus-specific IgG antibodies where baseline is Screening visit of parent study). For study participants treated with placebo in the parent study : Baseline visit (Day 1) in CIDP04, except for Tetanus- and influenza A virus-specific IgG antibodies where baseline is Screening visit if applicable

Table 3–1: Expected Baseline

Measurement	Definition of Baseline
Pharmacodynamical variables: 
• Total serum IgG• NF-L levels	For study participants treated with rozanolixizumab in parent study CIDP01, refer to baseline definition in SAP for the parent study (ie for Total serum IgG: Baseline visit (Day 1) of parent study, if missing Screening visit of parent study. For study participants treated with placebo in the parent study: Total serum IgG: Baseline visit (Day 1) in CIDP04, if missing Screening visit (where applicable) NF-L: Baseline visit (Week 1) in CIDP04

ADA=anti-drug antibody; C3=complement component 3; C3a=complement component 3a; C4= complement component 4; C5a= complement component 5a; CIDP=chronic inflammatory demyelinating polyradiculoneuropathy; CIDP PRO=CIDP PRO instrument; ECG=electrocardiogram; IgG=immunoglobulin G; IgA=immunoglobulin A; IgE=immunoglobulin E; IgM=immunoglobulin M; INCAT=Inflammatory Neuropathy Cause and Treatment; iRODS=inflammatory Rasch-built Overall Disability Scale; NF-L=neurofilament light chain; PGIC=Patient Global Impressions of Change ; PGIS=Patient Global Impressions of Severity; RT-MRC=Rasch-built, modified-interval Medical Research Council scale.

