3.6 Treatment assignment and treatment groups

All study participants will receive rozanolixizumab in the OLE.

Analyses will be performed by treatment group and for all study participants where stated. The treatment groups will be displayed as follows in the TFLs:

- Treatment group 1: Newly treated (ie, study participants treated with placebo in parent study)
- Treatment group 2: Previously treated (ie, study participants treated with rozanolixizumab in parent study)

Participants with the reduced dose due to tolerability issues will be mapped under the same treatment groups. These study participants will be flagged in the listings. For the Observation period the same treatment groups will be displayed.

It is expected that study participants will have received treatment as randomized in CIDP01 and hence safety and efficacy analyses will be based on the randomized treatment group in CIDP01. However, if after unblinding of CIDP01 it is determined that a study participant has received

treatment different to the treatment they were randomized to, then for safety analyses the study participant will be allocated according to the actual treatment they received.

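### For newly treated participants who enter directly, SAP Table 3-1 names no obtainable vaccine-titre baseline and does not name CIDP01 Visit 16 as the NF-L baseline

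*SAP*

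**What the plan says.** SAP 3.6 defines the newly treated group as those who had placebo in CIDP01. For them the general rule in SAP 3.3 takes the CIDP04 value, "Visit 2 or if missing, the Screening Visit value (if applicable"). Table 3-1 then gives measurement-specific rules. For NF-L it says "NF-L: Baseline visit (Week 1) in CIDP04", with no fallback. For the immunological variables it uses the CIDP04 Baseline visit, "except for Tetanus- and influenza A virus-specific IgG antibodies where baseline is Screening visit if applicable".

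On sampling, Protocol 5.1 says of CIDP01 participants who complete treatment without relapse: "Study participants will enter CIDP04 on the same day as the last study visit in CIDP01: Visit 17". Protocol 8.1 says "The Screening Visit is only for study participants with a gap period between the parent study and entry in CIDP04", and lists vaccine titres there. The Visit 2 list in Protocol 8.2.1 has no titre. It does list NF-L, but for direct entrants with a parent value at the last visit "or at Visit 16 for NF-L), the assessment will not be repeated".

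SAP 3.1 fills Week 1 with parent data only when the assessment was done at the last parent visit. SAP 2.2 and Protocol Section 4 give every direct entrant the CIDP01 Baseline for all variables, whichever arm they were in.

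**The concern.** Change from Baseline in vaccine antibodies is a listed immunological variable, and SAP 9.3.6 summarises it by treatment group. Change in NF-L is a listed pharmacodynamic variable (SAP 2.2.2.4), and Protocol 14.4.3 includes NF-L among the variables to be tabulated.

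If the baseline rule points to a sample that part of the newly treated group never gives, the change summary no longer describes that group. Inclusion criterion 2 offers CIDP01 participants two routes into the study: completing treatment without relapse and entering directly, or relapsing and being rescued and stabilised first. Losing the direct entrants leaves the relapsed, re-stabilised gap entrants. They must be on stable immunoglobulin at entry (inclusion criterion 6), and immunoglobulin is then prohibited during treatment (Protocol 7.8.2). Their titre change may therefore also reflect immunoglobulin withdrawal.

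**Working it through.** The plan states no figure to reproduce. The check follows a newly treated direct entrant through the baseline rules. Sampling visits come from Protocol 8.1 and 8.2.1, because the columns of Table 5-1 did not survive text extraction reliably.

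| Step | Vaccine titres | NF-L |
|---|---|---|
| Baseline named in SAP Table 3-1 | CIDP04 Screening, if applicable | CIDP04 Week 1 |
| CIDP04 Screening sample | None: no Screening Visit | Not listed in 8.1 |
| CIDP04 Visit 2 sample | Not in the 8.2.1 list | Listed, but skipped if a CIDP01 Visit 16 value exists |
| Carry-over under SAP 3.1 | Only if CIDP01 Visit 17 included titres, which is not stated | Visit 16 is not the last parent visit (Visit 17) |
| Result under SAP 3.3 and Table 3-1 | No baseline | Fresh Visit 2 value, or a Visit 16 value that the SAP wording does not reach |

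**Titres.** If the exception in Table 3-1 is read as falling back to Visit 2 when there is no Screening Visit, the result is the same, because no titre is scheduled there. The first scheduled CIDP04 titre for a direct entrant is at Visit 8 (Week 7), on drug. A CIDP01 value does exist: Table 3-1 uses the CIDP01 Screening titre for the previously treated group.

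**NF-L.** SAP 3.3 notes that the Visit 2 value may be the last one registered in CIDP01, but the reason it gives is that the two visits can coincide. That fits Visit 17, not Visit 16. Table 5-1 footnote f also waives only assessments done at the last parent visit, whereas Section 8.2.1 adds Visit 16 for NF-L. Practice at Visit 2 could therefore vary.

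**SAP 2.2 against 3.3.** For the same participant, 2.2 gives the CIDP01 Baseline and 3.3 gives the CIDP04 Baseline. The result is an older parent value or a missing one, depending on the section followed. SAP 3.9 does not record a departure from Protocol Section 4.

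**Age of a CIDP01 Screening titre.** The Protocol Introduction gives CIDP01 a Screening Period of 2 to 5 weeks and an 11-week Treatment Period. Assuming entry at the end of treatment, age at entry = screening + treatment: 2 + 11 = 13 weeks to 5 + 11 = 16 weeks.

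**The 33% rule.** SAP 4.2.4 withholds descriptive statistics when more than 33% of data points at a timepoint are missing. Suppose this applies to change values, with d direct and g gap entrants, and only the d values missing. The summary is withheld when d/(d + g) > 0.33, that is d > (0.33/0.67) × g ≈ 0.49 × g, or roughly more than one direct entrant for every two gap entrants. The group sizes are redacted, so which side of this line the study falls on is unknown.

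**The case against.** A reader might infer that newly treated direct entrants have no baseline for either variable anywhere in the SAP, and that 100% of their change values are lost for both. The documents do not support that. NF-L is scheduled at Visit 2 and omitted only when a CIDP01 Visit 16 value exists. The protocol clearly means that value to stand in, and the SAP follows the protocol unless it says otherwise. SAP 2.2 would also supply a parent baseline for both variables. What remains is a missing reference for NF-L, a real absence for titres under 3.3, and a contradiction between two SAP sections.

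Protocol 14.2 says "Baseline will be the last nonmissing data collected prior to the first dose of IMP", which would admit CIDP01 values for placebo participants. The same sentence leaves measurement-specific baselines to the SAP, so it supports the proposed change but does not require it.

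The consequences are also limited. Both variables serve exploratory objectives in a descriptive single-arm study. SAP 9.2 specifies outputs for IgG only, so an NF-L change table rests on Protocol 14.4.3. Absolute titres are still summarised for everyone. A change table confined to gap entrants is not certain either, since the 33% rule may suppress it.

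Finally, a CIDP01 Screening titre is an imperfect baseline. It is old, and it comes from people maintained on immunoglobulin, so a change from it could mix altered immunoglobulin exposure with drug effect. That objection stands, and a flag discloses the problem without removing it.

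**Conclusion.** The point holds for vaccine titres under SAP 3.3 and Table 3-1. By design, every newly treated direct entrant lacks a titre baseline unless an unscheduled pre-dose titre was taken, which SAP 3.3 would accept. If CIDP01 Visit 17 included titres, SAP 3.1 would supply a Week 1 value, but Table 3-1 would still point to Screening.

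For NF-L the fault is narrower. A usable value exists, and only a literal reading of the carry-over wording drops it. The conflict between SAP 2.2 and 3.3 is genuine and reaches beyond these two variables, because both sections claim to cover all of them.

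The number of participants affected cannot be given. The point is worth correcting because it costs little and recovers collected data, but it does not touch the primary safety analysis.

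**What to change.** In SAP Table 3-1, for newly treated participants who enter directly:

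- **Titres:** use the last CIDP01 titre before the first rozanolixizumab dose. CIDP01 Screening is the only timepoint these documents show, and it is the one already used for the previously treated group.
- **NF-L:** name the CIDP01 Visit 16 sample as the Week 1 value when NF-L was not repeated at Visit 2. This covers either reading of footnote f and Section 8.2.1.
- **Flag:** mark titres from CIDP01 Screening and titres taken on immunoglobulin, and state the caveat with the change summary.

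Reconcile SAP 2.2 with 3.3 by stating which section governs, and record any departure from Protocol Section 4 in SAP 3.9.

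The cost is SAP wording and programming, with no new samples. The downside is a titre baseline that may be about 13 to 16 weeks old and taken on immunoglobulin, so the change for these participants cannot be read as drug effect alone.

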3.4 Protocol deviations

Important protocol deviations (IPDs) are deviations from the protocol which potentially could have a meaningful impact on study conduct or on the primary efficacy, key safety, or PK/PD outcomes (if applicable) for an individual participant. The criteria for identifying important protocol deviations will be defined in the protocol deviations specifications. Important protocol deviations will be reviewed as part of the ongoing data cleaning process and data evaluation. All IPDs will be identified and documented prior to unblinding to confirm exclusion from analysis sets.

IPDs potentially related to the Coronavirus Disease 2019 (COVID-19) will be identified via a specific eCRF page "COVID-19 Impact" per visit with relationship: confirmed, suspected infection, general circumstances around or any other deviation from the protocol due to COVID-19. These deviations will also be reviewed separately as part of the ongoing data cleaning process.

3.5 Analysis sets

3.5.1 Enrolled Set

The Enrolled Set (ES) will consist of all study participants who have signed the informed consent form.

3.5.2 Safety Set

The Safety Set (SS) will consist of all enrolled study participants who were administered at least one dose of rozanolixizumab in CIDP04.

All safety variables will be analyzed using the SS.

3.5.3 Full Analysis Set

The Full Analysis Set (FAS) will consist of all participants in the SS, who have a Baseline and at least one valid post-Baseline iRODS measurement up to Visit 26/PEOT (inclusively).

Measurements are considered invalid if the participant received rescue medication before the assessment of iRODS. Assessments collected at the same day as first intake of rescue medication are considered valid. Invalid measurements will not be used for summary tables, but kept in listings.

3.5.4 Modified Full Analysis Set

The Modified Full Analysis Set (MFAS) will consist of all participants in the FAS, excluding any participant who either:

- received a mean actual dose of IMP deviating $>10\%$ or $<-10\%$ from the total planned dose
- missed more than two administrations in a period of three months.

The definition of the dose as well as details for calculations are provided in Section [Error! Reference source not found.](#)

3.5.5 Pharmacokinetic Per-Protocol Set

The Pharmacokinetic Per-Protocol Set (PK-PPS) is a subset of the SS, consisting of those participants who had no important protocol deviation affecting the plasma concentration of rozanolixizumab. Post-Baseline deviations will not necessarily lead to total exclusion of a participant from the PK-PPS but may lead to exclusion of specific data.

